# 8.2.11 Subject hotline

Subjects will be provided with contact details for a Subject Hotline, which can be used to contact the trial site during their participation in the trial should they require guidance or should they experience any symptoms of illness. The reporting of any symptoms of illness, e.g., flu-like symptoms, may trigger diagnostic measures (including ad hoc site visits) at the discretion of the investigator. For guidance for specific AEs, see Section 6.6.3.

# 8.2.12 Subject wellbeing questioning

Structured non-leading subject wellbeing questioning will be performed at the times given in the SoA (Section 1.3). Subject responses may trigger more in-depth questioning on specific topics, and may trigger diagnostic measures (including ad hoc site visits) at the discretion of the investigator.

# 8.2.13 Assessment of systemic reactions

Systemic reactions after IM immunization will be assessed via daily solicited reports in the subject diaries and at the times given in the SoA (Section 1.3).

BioNTech SE Confidential	Clinical Trial Protocol	Page 74 of 113
	including Amendments Nos. 01 to 09	Version: 13.0
	BNT162-01	Date: 12 JAN 2022

Systemic reactions will be graded using criteria based on the guidance given in US FDA Guidance for Industry "Toxicity Grading Scale for Healthy Adult and Adolescent Volunteers Enrolled in Preventive Vaccine Clinical Trials" for "Systemic reaction grading scale" (see the section "Assessment of intensity" in Section 10.3.1.11).

# 8.3 Adverse events and serious adverse events

The investigator and any qualified designees are responsible for detecting, documenting, and recording events that meet the definition of an AE or SAE and remain responsible for following up all AEs and SAEs.

# 8.3.1 Time period and frequency for collecting AE and SAE information

For Cohorts 1 to 10, all AEs and SAEs will be collected from the date of subject consent until discharge from the trial only IMP-related AEs and any SAEs will be collected.

For Cohorts 11 to 13 and 14, all AEs and SAEs will be collected from the date of subject consent until Visit 7 (the EoT Visit). From Visit 7 through 9 only IMP-related AEs, SAEs, and SARS-CoV-2 infections will be collected. After Visit 9 (e.g., Visits 10, 11, and 12) until the last scheduled FU Visit (i.e., when the subject is discharged from the trial), any SARS-CoV-2 infections and SAEs will be collected.

For subjects in Cohorts 11 to 13 who receive a non-trial SARS-CoV-2 vaccination, AEs/SAEs will be collected as specified above until the date when the subject was vaccinated with the non-trial SARS-CoV-2 vaccine. The AEs expected to be captured after non-trial SARS-CoV-2 vaccination are within the frame of post-marketing safety data reporting.

All SAEs (initial and follow-up reports) will be recorded and reported to the sponsor or designee within 24 h after becoming aware of the event, as indicated in Section 10.3.1.10.

Investigators are not obligated to actively seek AEs or SAEs after conclusion of the trial participation. However, if the investigator learns of any SAE, including a death, at any time after a trial subject has been discharged from the trial, and he/she considers the event to be reasonably related to the IMP administration or trial participation, the investigator must promptly notify the sponsor.

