## 1.3 Schedule of activities

Table 6: Schedule of trial procedures and assessments – BNT162a1, BNT162b1, BNT162b2, and BNT162c2 when tested P/B (excluding Cohorts 11 to 14)

Procedure / Assessment	Visit 0	Visit 1 Pre- dose	Visit 1 (Post-) dosing	Visit 2 at 24±2 h	Phone call at 48±2 h	Visit 3	Visit 4 Pre- dose	Visit 4 Dosing & Post- dose	Phone call at 48±2 h	Visit 5	Visit 5a	Visit 6	Visit 7 (EoT Visit)	Visit 8 (FU Visit)	Visit 9 (FU Visit)
Day h	-30 to 0	1	1	2		8	22	22		29	36 q	43	50 r	85	184
Days to last dose h		0	0			7	21	0		7	14	21	28	63	162
Informed consent	Х														
Inclusion/exclusion criteria	x	X (review)													
Medical history	х	X (update)													
Physical examination incl. height	х	X a		X a		X a	X a			X a		X a	X a		
Vital signs, body weight c	x	х	X p	х		х	х	Xp		х		х	х	х	х
12-lead ECG	Х	Х													
Urine pregnancy test for WOCBP	х	x					х								
Urine drugs of abuse screen d	х	x													
Alcohol breath test	Х	Х													
Urine collection for clinical laboratory e	х	х		х		х				х			х		
Blood draw for clinical laboratory (15 mL) f	х	х		х		х				х			х		
Blood draw for viral screening g	X (5 mL)														

BioNTech SE
Confidential

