- f) Clinical laboratory tests: (Chemistry) alkaline phosphatase, creatinine, ferritin, C-reactive protein, albumin, alanine aminotransferase, amylase, aspartate aminotransferase, gamma glutamyl transpeptidase, total bilirubin, blood urea nitrogen, glucose, lipase, sodium, potassium, calcium; (Hematology) hemoglobin, hematocrit, red blood cell count, white blood cell count and differential (neutrophils, lymphocytes, monocytes, eosinophils, basophils), platelet count. Only in women who are not WOCBP (to confirm postmenopausal status): follicle stimulating hormone at Visit 0.
- g) Viral screening for human immunodeficiency virus (HIV) 1 or 2, hepatitis B, hepatitis C.
- h) Flexibility for visit days: Visit 3 Day 8±1 d; Visit 4 Day 22±2 d; Visit 5 Day 29±3 d; Visit 6 Day 43±4 d; Visit 7 Day 50±4 d; Visit 8 Day 85±7 d; Visit 9 Day 184±9 d.
- i) Only for the first 6 subjects per group. Questioning on and documentation of AEs as well as systemic and local reactions, the latter in case of upcoming dose decision meetings.
- j) Only IMP-related AEs and any SAEs except proven COVID-19 cases which have to be reported regardless on severity and relatedness to the trial drug until the last scheduled FU Visit as described in Section 10.3.1.9.
- k) Blood draw for anti-SARS-CoV-2 antibodies.
- I) For Cohorts 1 and 8, immunization with at least 1 h intervals between subjects for the first 6 subjects and then with of at least 30 min intervals for the remaining 6 subjects. For all other cohorts and for all boost immunization, the intervals between subjects will be at least 30 min.
- m) Oral swipe for SARS-CoV-2 testing either on Day -1 or at the Visit 1 on Day 1.
- n) The timing of the listed "research" blood draw days may be adapted within the 200 mL maximum volume if justified by the collected data. Leftover blood after completion of the immunogenicity assessments may be used for additional analyses as described in Section 8.7 (Genetics) and/or Section 8.8 (Biomarkers).
- For subjects who have given consent, one aliquot of the blood sample drawn for analysis of CMI may be used for HLA typing to allow additional analysis of T-cell receptor repertoire and/or phenotypic characterization of T cells specific to vaccine-encoded antigens.
- p) If HLA typing using the blood sample collected with Lithium Heparin is not conclusive, EDTA-blood will be drawn for HLA testing.
- q) Only cohorts starting prime dosing after approval of protocol amendment 06.

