- f) Clinical laboratory tests: (Chemistry) alkaline phosphatase, creatinine, ferritin, C-reactive protein, albumin, alanine aminotransferase, amylase, aspartate aminotransferase, gamma glutamyl transpeptidase, total bilirubin, blood urea nitrogen, glucose, lipase, sodium, potassium, calcium; (Hematology) hemoglobin, hematocrit, red blood cell count, white blood cell count and differential (neutrophils, lymphocytes, monocytes, eosinophils, basophils), platelet count. Only in women who are not WOCBP (to confirm postmenopausal status): follicle stimulating hormone at Visit 0.
- g) Viral screening for human immunodeficiency virus (HIV) 1 or 2, hepatitis B, hepatitis C.
- h) Flexibility for visit days: Visit 3 Day 8±1 d; Visit 4 Day 22±2 d; Visit 5 Day 29±3 d; Visit 5a Day 36±3 d; Visit 6 Day 43±4 d; Visit 7 Day 50±4 d; Visit 8 Day 85±7 d; Visit 9 Day 184±9 d; Visit 10 Day 365±14 d; Visit 11 Day 547±14 d; Visit 12 Day 730±14 d.
- i) Only for HIV-positive subjects (done locally).
- j) Visits 8 and 9, only IMP-related AEs and any SAEs. Visits 10, 11, and 12, only any SAEs except proven COVID-19 cases which have to be reported regardless on severity and relatedness to the trial drug until the last scheduled FU Visit as described in Section 10.3.1.9. For subjects who receive non-trial SARS-CoV-2 vaccinations, the AEs expected to be captured after these vaccinations are within the frame of post-marketing safety data reporting (see Section 8.3.1).
- k) Blood draw for anti-SARS-CoV-2 antibodies.
- I) For first immunization in Cohort 13, immunization with at least 30 min intervals between the primary immunizations and 30 min between the boost immunizations. For Cohorts 11 and 12, the interval between the trial subjects will be at least 15 min for the prime immunizations and at least 5 min for the boost immunizations.
- m) Oral swipe for SARS-CoV-2 testing either on Day -1 or at the Visit 1 on Day 1.
- n) The timing of the listed "research" blood draw days may be adapted (within the 200 mL maximum volume) if justified by the collected data. Leftover blood after completion of the immunogenicity assessments may be used for additional analyses as described in Section 8.7 (Genetics) and/or Section 8.8 (Biomarkers). For subjects who receive non-trial SARS-CoV-2 vaccinations, there will be no blood sampling for immunogenicity or cell-mediated immune testing in the FU Visits.

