c) Vital signs: systolic/diastolic blood pressure, pulse rate, respiratory rate, and body temperature; body weight only at Visit 0.

d) Urine screening for drugs of abuse (amphetamines, benzodiazepines, barbiturates, cocaine, cannabinoids, opiates, methadone, methamphetamines, phencyclidine, tricyclic antidepressants).

e) Dipstick urine analysis: glucose, bilirubin, ketone, specific gravity, blood, pH, protein, urobilinogen, nitrite, and leukocytes. Microscopic urinalysis: if warranted by dipstick results, urine sediment will be microscopically examined for the presence of red blood cells, white blood cells, casts, crystals, epithelial cells, and bacteria.

f) Clinical laboratory tests: (Chemistry) alkaline phosphatase, creatinine, ferritin, C-reactive protein, albumin, alanine aminotransferase, amylase, aspartate aminotransferase, gamma glutamyl transpeptidase, total bilirubin, blood urea nitrogen, glucose, lipase, sodium, potassium, calcium; (Hematology) hemoglobin, hematocrit, red blood cell count, white blood cell count and differential (neutrophils, lymphocytes, monocytes, eosinophils, basophils), platelet count. Only in women who are not WOCBP (to confirm postmenopausal status): follicle stimulating hormone at Visit 0.

g) Viral screening for human immunodeficiency virus (HIV) 1 or 2, hepatitis B, hepatitis C.

- h) Flexibility for visit days: Visit 3 Day 8±1 d; Visit 3a Day 15±2 d; Visit 4 Day 22±2 d; Visit 5 Day 29±3 d; Visit 7 Day 50±4 d; Visit 9 Day 184±9 d.
- i) Visit 9, only IMP-related AEs and any SAEs. Proven COVID-19 cases which have to be reported regardless on severity and relatedness to the trial drug until the last scheduled FU Visit as described in Section 10.3.1.9.
- j) Blood draw for anti-SARS-CoV-2 antibodies.
- k) Oral swipe for SARS-CoV-2 testing either on Day -1 or at the Visit 1 on Day 1.
- The timing of the listed blood draw days may be adapted, as long as the total volume drawn does not change, if justified by the collected data. Leftover blood after completion of the immunogenicity assessments may be used for additional analyses as described in Section 8.7 (Genetics) and/or Sections 8.8 and 8.9 (Biomarkers).
- m) If HLA typing using the blood sample collected with Lithium Heparin is not conclusive, EDTA-blood will be drawn for HLA testing.

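### In boosted subjects, all-AE collection stops at Visit 7, which may fall up to 4 or 6 days before the primary TEAE interval ends

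*Protocol*

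**What the plan says.** **Collection.** For Cohorts 11 to 14, Protocol 8.3.1 states that "all AEs and SAEs will be collected from the date of subject consent until Visit 7 (the EoT Visit", and then: "From Visit 7 through 9 only IMP-related AEs, SAEs, and SARS-CoV-2 infections will be collected". The schedule of activities (Protocol 1.3) puts the same limit on the AE-recording row:

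- Table 6 footnote j (dose-ranging P/B cohorts, Visits 8 and 9): "Only IMP-related AEs and any SAEs except proven COVID-19 cases", the COVID-19 cases being reportable in any event.
- Table 8 footnote j (Cohorts 11 to 13): "Visits 8 and 9, only IMP-related AEs and any SAEs".
- Table 9 footnote i (Cohort 14): "Visit 9, only IMP-related AEs and any SAEs".

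The 8.3.1 sentence for Cohorts 1 to 10 ends "until discharge from the trial only IMP-related AEs and any SAEs will be collected" and names no cut-off visit. For those cohorts the limit therefore rests on Table 6.

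**Timing.** Footnote h of Tables 6, 8 and 9 gives the boost (Visit 4) as Day 22±2 and Visit 7 as Day 50±4 (Table 6: "Visit 7 Day 50±4 d; Visit 8 Day 85±7 d"). The superscript h marks both the trial-day row and the row "Days to last dose", in which Visit 7 stands at 28.

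**Analysis.** Protocol 3 ends the primary unsolicited-TEAE endpoint for P/B regimens 28 d after the boost, trial day 50. Protocol 9.4.2 analyses AEs from the boost to 28 d after it. Protocol 10.3.1 makes relatedness matter only for onset more than 28 d after the last dose. SAP 6.4.3 assigns TEAEs by start date and time to an interval from the actual boost to day 28 inclusive. SAP 6.1.1 uses the analysis-set N as denominator unless stated otherwise.

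**Conflicting text.** Protocol 10.3.1.7 requires any AE, related or not, to be documented until the later of 21 d after the last immunization and discharge. Protocol 10.3.1.10, on the paper SAE form, refers to 8.3.1 for the period of observation.

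**The concern.** The collection rule is tied to a visit with a tolerance, while the analysis interval is tied to a fixed number of days after the actual boost. If Visit 7 is early, the last days of the primary interval are collected under the restricted rule, but the subject still counts fully in the denominator. An unrelated, non-serious, non-COVID AE that starts after Visit 7 and by day 28 belongs in the proportion but is not requested. It changes the proportion only if the subject has no earlier counted event.

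Any error is therefore downward, in a primary safety proportion. It can also differ between cohorts with different visit timing, and nothing in the planned output would show it.

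**Working it through.** **1. The plan's own figure.** Nominal boost on Day 22 plus 28 d is Day 50, as Protocol 3 states. At nominal days there is no gap.

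**2. Tolerance in trial days.** The boost falls on Day 20 to 24 and Visit 7 on Day 46 to 54.

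- Shortest distance: 46 − 24 = 22 d. Longest: 54 − 20 = 34 d.
- Largest gap before day 28: 28 − 22 = 6 d. With the boost on Day 22 it is 50 − 46 = 4 d.
- Permitted day pairs under 28 d, for boost Days 20, 21, 22, 23 and 24: 2 + 3 + 4 + 5 + 6 = 20 of 5 × 9 = 45.

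**3. Tolerance from the last dose.** Visit 7 falls 28 ± 4 = 24 to 32 d after the boost. It is under 28 d on 4 of 9 permitted days (24, 25, 26, 27), with a gap of at most 28 − 24 = 4 d.

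The counts in steps 2 and 3 show what the windows permit, not how often it happens.

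**4. Who is not affected.** For BNT162c2 single dose, all AEs are recorded to Visit 6, Day 43±4 (Day 39 to 47). That is 38 to 46 d after the Day 1 dose, beyond the 28 d interval. For P/B subjects without a boost, the SAP interval ends 28 d after prime (Day 29), well before the earliest Visit 7 (Day 46).

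**5. Other sources for the gap.** Tables 6 and 8 issue diaries at Visit 7 and collect them at Visit 8, so some reports may still arrive in the P/B groups of Cohorts 1 to 13. Table 9 issues none at Visit 7 in Cohort 14. The next scheduled visit is nominally 85 − 50 = 35 d after Visit 7, or 184 − 50 = 134 d in Cohort 14.

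**6. Size, by assumption only.** The documents give no rate of unrelated events. Assume a constant onset rate, all events unrelated and non-serious, every subject seen on the earliest permitted day, and a true 28-day proportion p. With all-AE collection to day t, the proportion is low by (1 − p)^(t/28) − (1 − p):

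| p | t = 24 d | t = 22 d |
|---|---|---|
| 20% | 2.6 points | 3.9 points |
| 30% | 3.7 points | 5.6 points |
| 50% | 5.2 points | 8.0 points |

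One subject in a 12-subject cohort is 1/12 = 8.3 points. At t = 22 the loss reaches that at p of about 54%. It peaks near p = 68%: 0.32^(22/28) − 0.32 = 0.4085 − 0.32, just under 9 points. The table is thus an assumption-based range. It is not a ceiling and not an estimate for this trial.

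**The case against.** **The days are declared approximate.** Footnote a to the SAP endpoint table says so and points to the schedule for assessment windows. This softens the nominal endpoint days. It does not change the day-28-inclusive rule in SAP 6.4.3 or the 28 d boundary in Protocol 10.3.1, so it does not close the gap.

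**Protocol 10.3.1.7 already requires all AEs until discharge.** On that text alone the gap is 0 d. But it then contradicts 8.3.1 and three schedule footnotes, and 10.3.1.10 points to 8.3.1 for the period of observation. That reference concerns SAE reporting, so it favours 8.3.1 without settling the matter.

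**The 6 d is a corner case.** True: it needs trial-day tolerances, a boost 2 d late and a Visit 7 that is 4 d early. The 4 d gap is possible on either reading.

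**The effect is small.** Accepted. Protocol 2.3.1 notes that many reported TEAEs resemble reactogenicity and typically begin within 24 h, so a constant onset rate with all events unrelated is an extreme assumption.

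Two stronger readings are tempting and are not supported:

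- *A delayed boost leaves a much larger gap.* Protocol 7.1.1 lets Cohorts 11 to 14 have the boost within 1 week of schedule. If Visit 7 stayed fixed, a Day 29 boost would leave 46 − 29 = 17 to 54 − 29 = 25 d, a gap of up to 11 d. But a fixed Visit 5 (Day 29±3) would then fall between 3 d before and 3 d after the boost, while the row "Days to last dose" requires 7. That row suggests that visits follow the boost, in which case step 3 applies. The text needs only clarification.
- *The SAP summary of any AE after day 28 cannot be filled.* It can, in part. Single-dose subjects, unboosted P/B subjects and boosted subjects with a late Visit 7 all have all-AE data past day 28, and related AEs, SAEs and COVID-19 cases continue to be collected. The table is incomplete for unrelated non-serious events once restricted collection begins; it is not empty.

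**Conclusion.** The point holds and is minor. For boosted P/B subjects, Protocol 8.3.1 (Cohorts 11 to 14) and the schedule's AE footnotes allow all-AE collection to end up to 4 d (tolerance from the last dose) or up to 6 d (tolerance in trial days) before the primary interval ends. Protocol 10.3.1.7 contradicts that restriction.

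The resulting bias is downward, of unknown and probably small size, in a descriptive endpoint with no hypothesis test. The day arithmetic rests only on the stated windows. The percentage-point range rests wholly on the assumptions in step 6. A reader might infer that fewer than one subject per 12-subject cohort could ever be lost; that holds only for true proportions up to about 54%, even under those assumptions. How many subjects actually had an early Visit 7 cannot be told from the documents.

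**What to change.** **Protocol.** Reconcile 8.3.1 (including the Cohorts 1 to 10 sentence), 10.3.1.7, footnote h and the AE footnotes of Tables 6, 8 and 9, so that all AEs are collected to the later of Visit 7 and 28 d after the last immunization. State whether visit tolerances run from the actual boost, and clarify whether Visit 7 moves when the boost is delayed under 7.1.1. Where Visit 7 is early, add a short AE contact, for example by phone, because the next scheduled visit is weeks or months later.

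**SAP.** Derive the days from last dose to the end of all-AE collection, and report by cohort how many boosted subjects have under 28 d. Optionally, add one sensitivity summary of the unsolicited-TEAE proportion among those with at least 28 d; the main analysis keeps all subjects. Label the summary of any AE after day 28 as incomplete for unrelated non-serious events once restricted collection begins.

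**Cost.** Reconciled wording, a brief contact for early Visit 7s, one derived variable, one count by cohort, a table note and at most one extra table. For data already collected, only the SAP part applies.

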# 8.3.2 Method of detecting AEs and SAEs

The method of recording, evaluating, and assessing causality of AEs and SAEs and the procedures for completing and transmitting SAE reports are provided in Section 10.3.

Care will be taken not to introduce bias when detecting AEs and/or SAEs. Open-ended and non-leading verbal questioning of the trial subject is the preferred method to inquire about AE occurrences.

# 8.3.3 Follow-up of AEs and SAEs

After the initial AE/SAE report, the investigator is required to proactively follow each trial subject at subsequent visits/contacts. All AEs/SAEs/DLTs will be followed until resolution, stabilization, the event is otherwise explained, or the trial subject is lost to follow-up (as

defined in Section 7.3). Further information on follow-up procedures is provided in Section 10.3.1.7.

The investigator is obligated to perform or arrange for the conduct of supplemental measurements and/or evaluations as medically indicated or as requested by the sponsor to elucidate the nature and/or causality of the AE or SAE as fully as possible. This may include additional laboratory tests or investigations, histopathological examinations, or consultation with other healthcare professionals.

New or updated information will be recorded in the originally completed CRF.

The investigator will submit any updated SAE data to the sponsor within 24 h of receipt of the information as indicated in Section 10.3.1.10.

All ongoing AEs/SAEs will be followed until resolution, considered by the investigator to be stable or chronic (resolved with sequelae), the trial subject is lost to follow-up or the trial subject withdraws consent. If no final status is reached by the time of discharge from the trial, the investigator must confirm the unavailability of a final status.

# 8.3.4 Regulatory reporting requirements for SAEs

Prompt notification of an SAE by the investigator to the sponsor is essential so that legal obligations and ethical responsibilities towards the safety of trial subjects and the safety of a trial treatment under clinical investigation are met.

The sponsor has a legal responsibility to notify both the local regulatory authority and other regulatory agencies about the safety of a trial treatment under clinical investigation. The sponsor will comply with country-specific regulatory requirements relating to safety reporting to the regulatory authority, Independent Ethics Committees (IECs), and investigators. The execution of expedited reporting to the different entities may be delegated as detailed in the trial Safety Management Plan.

Safety reports will be prepared for SUSARs according to local regulatory requirements and sponsor policy and forwarded to investigators as necessary.

For the IMP, it is the sponsor's or delegate's responsibility to perform SUSAR reporting to the regulatory authority, the IEC and the other investigators as required by national law and applicable guidelines.

An investigator who receives an investigator safety report describing an SAE or other specific safety information (e.g., summary or listing of SAEs) from the sponsor should review it and then file it together with the IB. If required by local requirements, the investigator will notify the relevant IEC.

